5.4.2 Analysis of Individual N-of-1 Trials

We will analyze each patient's trial of a specific trigger using the same methods as in Aim 1 applied to the outcomes of frequency, severity and duration of events reported daily. Frequency will be analyzed as a binary event on each day. Severity and duration will be analyzed as a mixture model between non-event days and event days with the mixture probability corresponding to the probability of an event.

5.4.3 Meta-Analysis of N-of-1 Trials

We will conduct separate meta-analyses of each set of N-of-1 trials that test a particular trigger. We expect this will likely be most relevant to the triggers offered in the menu which patients are more likely to try and which were also the most commonly identified triggers in a survey recently sent to 1,000 AF patients. The meta-analyses will use the same Bayesian multilevel methods as those outlined in Aim 1 and will be applied to the outcomes of AF events, duration and severity as well as the safety endpoints listed in Table 2. We will use distribution and link functions appropriate to the scale of each outcome variable. We will calculate the average treatment effect in the group of patients as well as the individual effects adjusted for the other patients.

Patients with AF are particularly interested in whether certain triggers are more likely than others to induce AF. Because patients in this study will be choosing to study different triggers and often will be conducting more than N-of-1 trial, the set of trigger comparisons will form a network of triggers (plus no trigger) that may be analytically compared using methods of network meta-analysis.²⁵ Triggers may then be compared indirectly through the common control using techniques from network meta-analysis. The complicating factor here is that trials done by the same patient will be correlated and it will be necessary to adjust for this correlation in the network meta-analysis model. This can be done in two different ways. The first would be to treat each patient's trials as separate and introduce a common patient effect into a Version 1.0 5/12/17

mixed model. The second would be to combine all the trials for a patient into one trial with several arms, one for each different trigger and one for no trigger that would combine all the results from the no trigger arms. If a patient changed the control (no trigger) arm in a new trial (e.g., by testing two triggers vs. one trigger), then the control arm would be analyzed according to the trigger used. This approach would create multi-arm trials for patients with multiple trials. These would then be analyzed by methods for multi-arm studies in a network meta-analysis.

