Meta-Analysis of N-of-1 Trials: The collection of individual N-of-1 trials can be thought of as a set of studies whose results can be combined as in a meta-analysis. The data can be considered as a multilevel structure in which a set of patients is studied with each patient having a set of measurements. Standard multilevel mixed model methods will be used to estimate the average effect and variance within and across patients. Across patient values estimate the average effect in the population of patients studied, while the within-patient estimates describe an improved estimate of each patient's true effect assuming exchangeability across patients. We will fit these models using a Bayesian multilevel model with non-informative priors in order to obtain posterior distributions of the within and between effect sizes. We will then compare the multilevel patient estimates with those from the patient's data alone in order to determine how much the effects change and how much additional precision these estimates gain.

Analysis of Comparative Effectiveness: The experimental design is a simple two-arm randomized trial comparing N-of-1 vs. symptom surveillance. The primary outcome is the change in the AFEQT scale from baseline to 12 weeks. The mean change in each treatment group will be compared by a t-test. The average frequency and severity of AF episodes per week during the final month of each participant's enrollment will be the secondary

outcomes. Their group means will also be compared with a t-test. We will check for balance in covariates across the randomized groups and will adjust for any imbalances by including those covariates in regression analyses and reporting the adjusted treatment effect as a secondary analysis.

Missing Data: A major purpose of this aim is to determine the feasibility and usability of N-of-1 studies for actual application in clinical practice. Therefore, carefully documenting adherence and completion rates and predictors of each will be an important aspect of this study. Within the HeH study, we have found that >90 % of all AF HeH study participants complete all AF-related surveys, including the AFEQT. The primary analysis will be intent-to-treat which uses all participants as randomized. When no endpoint is available, we will assume no change. Further analyses will employ multiple imputation to fill in missing values, particularly in covariate-adjusted models ([name]-3).

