4.1 Measures

Data that will be collected during the study are detailed in Table 2:

Construct	Measure(s)	Categorization	Timing	Source	
Primary Outcome (comparing N-of-1 group to data tracking group)					
Atrial fibrillation quality of life	AFEQT score	Integer (20-140). Survey includes 20 questions 1-7	Baseline and 10 weeks	Eureka app	
		score for each			
Primary Outcomes	(for individual-level	N-of-1 trials within th	e N-of-1 group)	Γ	
Atrial fibrillation	ECG flagged by	1=Yes	Daily and whenever	AliveCor app	
device	algorithm	U=INO	a symptomatic		
Atrial fibrillation	Patient report	1=Yes 0=No	Daily	Eureka app	
Atrial fibrillation duration	Patient report (hrs and minutes)	Integer 0-60 hrs, 0-60 min	Daily (queried only if self-reported atrial fibrillation=Yes on that day)	Eureka app	
Atrial fibrillation severity	Patient report	Integer 1-7, ordinal scale 1=least severe	Daily (queried only if self-reported atrial fibrillation=Yes on that day)	Eureka app	
SECONDARY ENDPOINTS					
AliveCor confirmed atrial fibrillation event	Patient reported atrial fibrillation event confirmed	1=Yes 0=No	Daily and whenever a symptomatic episode occurs	AliveCor app and Eureka app	

Table 2

within the N-of-1 group and compared to data tracking in last	by report from AliveCor device			
Count of AF Frequency	The number of patients reported AF episodes during the final month of enrollment	Integer 0-7—count	Daily	Eureka app
Total duration of AF episodes	Total duration of patient reported AF episodes daily during the final month of enrollment	Continuous 0-60 min, 0-24 hours 0= no answer	Daily (only if self-reported atrial fibrillation=Yes on that day)	Eureka app
Average severity of AF episodes	average severity of patient reported AF episodes daily during final month of enrollment	Continuous (range 1-7 using, Ordinal Scale 1=least severe 0= no answer	Daily (only if self-reported atrial fibrillation=Yes on that day)	Eureka app
Safety Measures Emergency room visit	Patient report	1=Yes 2=No 3=Don't know If yes, date and hospital location	Monthly: Reported at 4 & 8 weeks; actual emergency room visits will be categorized by day	Eureka app
Emergency room visit related to atrial fibrillation	Patient report	1=Yes 2=No 3=Don't know	Monthly (queried only if emergency room visit=Yes for that month) Reported at 4 &8 weeks.	Eureka app

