4.4. Safety Endpoints

- 1. **Hospitalization** Days on which any hospitalization occurs together with date and hospital location. This will be recorded from the Eureka app and will be reported monthly by the patient.
- 2. **Hospitalization related to atrial fibrillation** Days on which a hospitalization related to atrial fibrillation occurs together with date and hospital location. This will be recorded from the Eureka app and will be reported monthly by the patient.
- 3. **Emergency department visit** Days on which any emergency department visit occurs together with date and hospital location. This will be recorded from the Eureka app and will be reported monthly by the patient.
- 4. **Cerebrovascular accident** Days on which any cerebrovascular accident occurs together with date and hospital location. This will be recorded from the Eureka app and will be reported monthly by the patient.
- 5. **Myocardial infarction** Days on which a myocardial infarction occurs together with date and hospital location. This will be recorded from the Eureka app and will be reported monthly by the patient.
- 6. **Heart failure** Days on which heart failure occurs together with date and hospital location. This will be recorded from the Eureka app and will be reported monthly by the patient using language from previous HeH surveys.

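### Per-trigger Bayesian models of stroke, MI and heart failure (SAP 5.4.3) would mostly return their prior, whose scale is unstated; use one pooled exposure-versus-elimination table instead

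*SAP*

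**What the plan says.** SAP 5.4.3 sets the unit of analysis: "We will conduct separate meta-analyses of each set of N-of-1 trials that test a particular trigger". It sets the method by reference: "The meta-analyses will use the same Bayesian multilevel methods as those outlined in Aim 1". The Aim 1 methods are not set out in either document, and the SAP names no prior. The same paragraph extends the models beyond AF outcomes: they "will be applied to the outcomes of AF events, duration and severity as well as the safety endpoints listed in Table 2". It promises both an average effect and patient-level effects.

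The prior is in the Protocol. In 1.7.2, under the meta-analysis of N-of-1 trials: "We will fit these models using a Bayesian multilevel model with non-informative priors". No distribution or scale follows, and that paragraph mentions neither safety endpoints nor per-trigger fits.

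The safety measures in SAP Table 2 are emergency visits, hospitalisation, cerebrovascular accident, MI and heart failure. They are self-reported ("Monthly: Reported at 4 & 8 weeks" for emergency visits) but dated. SAP 4.4 defines stroke as "Days on which any cerebrovascular accident occurs together with date and hospital location" and MI as "Days on which a myocardial infarction occurs together with date and hospital location".

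Neither document sets a minimum event count, a prior sensitivity analysis or a descriptive-only rule for sparse endpoints. SAP 5.4.1 separately compares the randomised arms on each safety event as a binary any-event outcome.

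**The concern.** Each per-trigger model contrasts exposure weeks with elimination weeks within participants. With daily AF reports there is something to estimate. With strokes or infarctions over six weeks per person there will usually be no event for a given trigger, and occasionally one. The likelihood then barely limits the effect on one side, so the posterior takes its shape from the prior on the effect and from the prior on between-patient heterogeneity. On a log scale a non-informative prior is not neutral here: the wider it is, the more firmly a single event is read as harm or as benefit, according to the week in which it happened to fall.

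At stake is a trigger-specific statement about a serious event that reflects an undocumented setting. Meanwhile the safety question specific to this intervention, whether weeks of instructed exposure carry more events than weeks of avoidance, is never addressed over all triggers together, which is where the few events would accumulate.

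**Working it through.** **Inputs from the documents.** 239 per arm (SAP 5.2); 6 weeks per N-of-1 trial, up to 3 on and 3 off (SAP 2); about 8 named triggers plus the patient's own choice (SAP 5.1), taken as 8 or 9; up to 5 triggers per participant in the N-of-1 arm and up to 4 after crossover (Protocol 1.5).

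**Assumed, because the documents give no safety rates.** Stroke or MI at 0.5 to 2 per 100 person-years; hospitalisation at 5 to 30.

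**The plan's own figure.** The plan gives no expected event count to reproduce. For the 239 used here, 2 × 19² × (1.960 + 0.842)² / 5² gives 227 per group for 80% power (two-sided 0.05), and 239 gives about 82%. The gap is conservative and has no bearing on this point.

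**Step 1: expected events.**
- Person-time: 239 × 6 / 52.18 = 27.5 person-years; per trigger 27.5/9 = 3.05 to 27.5/8 = 3.44.
- Stroke or MI, all triggers: 27.5 × 0.005 = 0.14 to 27.5 × 0.02 = 0.55.
- Stroke or MI, per trigger, even spread: 3.05 × 0.005 = 0.015 to 3.44 × 0.02 = 0.07.
- If all 478 tested the same trigger once: 478 × 6 / 52.18 = 55.0 person-years. One expected event then needs 1/55.0 = 1.8 per 100 person-years.
- If every participant ran the maximum number of trials: 239 × (5 + 4) × 6 / 52.18 = 247.3 person-years, or 27.5 per trigger over 9. That is 0.14 to 0.55 stroke or MI events per trigger.
- Hospitalisation, 239 participants, one trial each: 0.15 to 0.92 per trigger with an even spread over 9, and 0.34 to 2.1 for a trigger chosen by 25%. For 25% of all 478 after crossover: 0.69 to 4.1.

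**Step 2: one event on, none off, equal time.** With log rate ratio b and no heterogeneity, the likelihood given one event is e^b/(1 + e^b). With prior N(0, s²), P(b > 0) = 2 ∫₀^∞ [e^b/(1 + e^b)] φ(b; 0, s) db.

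To come closer to the planned multilevel model, I also fitted a Poisson model with 30 patients on the trigger (239/8 ≈ 30), 3 weeks on and 3 off, a common log rate when off, and patient effects b_i ~ N(b, σ²). The priors on σ are my assumptions.

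| Model | Setting | P(harm) |
|---|---|---|
| No heterogeneity | s = 1 | 0.67 |
| No heterogeneity | s = 2.5 | 0.81 |
| No heterogeneity | s = 10 | 0.945 |
| No heterogeneity | s = 31.6 | 0.98 |
| No heterogeneity | s = 100 | 0.994 |
| Event share, Beta(1,1) | 1 − 0.5² | 0.75 |
| Event share, Jeffreys | | 0.82 |
| Random effect, σ uniform(0, 2.5) | s = 10, intercept SD 100 | 0.90 |
| Random effect, σ uniform(0, 2.5) | s = 100, intercept SD 100 | 0.98 |
| Random effect, σ uniform(0, 10) | s = 10, intercept SD 10 | 0.50 |
| Random effect, σ uniform(0, 10) | s = 10, intercept SD 100 | 0.66 to 0.67 |
| Random effect, σ uniform(0, 10) | s = 100, intercept SD 100 | 0.91 to 0.92 |

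With no heterogeneity and s = 31.6, the 95% interval for b is 0.53 to 70.8, which excludes zero on a single event. At s = 10 it is −0.97 to 22.4. An event in an elimination week gives a similar probability of apparent benefit.

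**Step 3: the exact reference.** With equal time, the probability that a single event falls in an exposure week is 0.5, so the one-sided p is 0.5. The exact 95% interval for the exposure share, from 1 of 1, is 0.025 to 1.

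**The case against.** The strongest reply is that the plan is multilevel with a random treatment effect, so calculations without heterogeneity exaggerate. That stands. A reader might infer that one event will read as near-certain harm; the documents do not support this. It needs a diffuse log-scale prior and limited heterogeneity, and neither is specified. What survives is the width of the range, which is the problem itself.

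Some other readings go further than the text allows:
- That the SAP prescribes the non-informative prior. Only the Protocol does; the SAP defers to Aim 1.
- That every safety endpoint has fewer than one event per trigger. This can fail for hospitalisation with popular triggers, repeat trials or crossover, and no count is available for emergency visits.
- That strokes are to be modelled as recurring weekly outcomes. SAP 5.4.3 promises a distribution and link suited to each outcome, and SAP 5.4.1 codes any event. That answers the scale of the outcome, not sparsity.
- That the trial lacks a safety comparison. SAP 5.4.1 compares the randomised arms, and SAP 4.7 sends hospitalisations and emergency visits to the DSMB. Only the pooled exposure-versus-elimination contrast is missing.
- That a posterior probability of harm per trigger is a promised output. SAP 5.4.3 promises effect estimates; the probability statement in Protocol 1.7.2 belongs to individual trials, which SAP 5.4.2 limits to AF frequency, severity and duration. P(harm) is used here as a summary of the posterior.

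It is also fair that a pooled stroke row may be empty. But an empty row is an accurate report, whereas a fitted effect from no events restates the prior.

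**Conclusion.** The concern holds for stroke and MI, and probably for heart failure. Expected counts are 0.015 to 0.07 per trigger under assumed rates of 0.5 to 2% per year, one trial per participant and an even spread. They stay below one per trigger with an even spread even if everyone runs the maximum number of trials. The resulting estimate would be set mainly by unstated prior and heterogeneity choices, with P(harm) from about 0.5 to 0.99 for the same single event. For hospitalisation and emergency visits the point is narrower: the plan needs a rule for when modelling is worthwhile. The primary endpoint and the randomised safety comparison are not affected, so this is a change the SAP should make and not a threat to the trial's main conclusion.

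**What to change.** In SAP 5.4.3:
- Remove stroke, MI and heart failure from the per-trigger models.
- Add one descriptive table over all triggers: first events dated to exposure weeks and to elimination weeks, the person-time in each, and an exact binomial interval for the exposure share set against the person-time split.
- Show hospitalisations and emergency visits in the same table. Fit per-trigger models to them only above a minimum event count stated before analysis, with the prior distributions and scales (treatment effect and heterogeneity) written down and a prior sensitivity analysis reported.
- Supply the table to the DSMB.

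The cost is SAP wording and less modelling than now planned. No new data item is needed, because the SAP already asks for event dates. The downside is that there would be no trigger-specific model estimates for the rare events, and the pooled stroke and MI rows may be empty or very imprecise.

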5.4.3.2 Heterogeneity of Treatment Effects

While N-of-1 trials are specifically constructed to evaluate individual treatment effects, it is also of interest whether particular triggers are more or less likely to have an effect on individuals with particular characteristics, particularly if the differential effects of triggers are moderated by modifiable factors or by individual characteristics that may indicate which triggers are most important. We will examine the set of modifiers listed in Table 2 that include medical history, demographics, medications, mood, stress and sleep by including these between-patient factors in the multilevel models.

5.4.3.3 Missing Data

Missing data in individual N-of-1 trials are likely going to be most pertinent to the daily measures of AF and duration and severity. We will treat days on which the patient makes no report as having no AF event. As with the analyses in Aim 1 with cases of missing outcome data, we will both ignore the missing values (assuming missing at random) and treat the missing values as latent parameters and estimate them as part of the Bayesian model assuming them to be missing at random. If we suspect that data are missing not at random (MNAR), we will construct MNAR models based on the appropriate missing data patterns to determine sensitivity of inferences to this assumption. If any data on effect modifiers are missing, we may also attempt multiple imputation, particularly if the number is large and the number of latent parameters to be estimated becomes too large.

6.Potential Impact:

6.1 Potential Risks & Protection Against Risks

- 1. Loss of Confidentiality: There is a minor risk related to loss of confidentiality of responses to questions asking for an assessment of the individual's physical condition. There is minimal risk of a loss of privacy if another person sees responses through the mobile platform. The primary reasons this would occur would be because a patient lost their device or if they provided another person access to their mobile device.
 - Patients will submit their data via SMS text messages, via mobile applications or via secure websites. SMS messages and mobile notifications are transmitted through 3rd party services (e.g., Twilio and Urban Airship). Simple, non-PHI carrying messages are sent by the system, and typically unidentifiable numeric responses are returned. The only PHI involved in the transaction is the phone number or unique ID used to identify the patient's phone. Patients can opt out of these mechanisms and respond entirely through a secure website if they choose.
 - The platform will also be able to communicate with commercial devices and other data sources managed by the patient (e.g., AliveCor). When logging into the platform, the patient can actively elect to allow the platform to communicate with these external data sources and devices. The use of these devices is elective and therefore not necessary in order to participate in the study. The patient will be responsible for the

security of these data when housed with the external vendor. Once data from these sites/devices are imported in the platform, data security procedures as previously described will apply.

- 2. Physical Risk: All patients will be instructed to follow their physician's advice regarding treatment of their AF. The number of symptomatic AF episodes and severity of these episodes (the main measures proposed in Aim 2 of this study and the target of behavioral modification strategies), while extremely troublesome for many patients are not a safety concern.²⁶ It is important to emphasize that AF is not an imminently dangerous rhythm and that the primary issue regarding safety is stroke and thromboembolic prophylaxis. Stroke and thromboembolic risk is not thought to be related to the number of AF episodes or potentially even AF episodes themselves. Specifically, per the AF guidelines, anticoagulation needs to be dictated by stroke risk score and not by whether AF is paroxysmal or persistent or based on the frequency of disease.²⁶ Recent trials with continuous monitoring of atrial activity have demonstrated that there is no relationship between the timing or duration of AF episodes and the timing of strokes that occur.²⁷ This is also supported by evidence from multiple randomized trials that have clearly demonstrated that a rhythm-control strategy (i.e., a strategy involving obtaining and maintaining normal sinus rhythm) does not protect against stroke.^{28,29} Therefore, changing potential triggers to reduce episodes primarily serves guality of life purposes and should not influence the overall safety of patients. The behavioral modification that patients will undertake as part of an N-of-1 trial is analogous to current recommendations that view strategies to obtain and maintain a normal rhythm (whether it be with drugs or invasive ablation) as a means to attain improved quality of life.
- 3. *Psychological Risk:* Patients and parents will be assured during the informed consent discussions that participation is voluntary. There may be a risk of psychological discomfort for patients associated with completion of the surveys, questionnaires, or other information required to conduct the trial, including feelings of embarrassment or distress when reviewing data with the doctor. They may also feel anxious or confused by using a device or web application that they would not have otherwise used if they had not been participating in the study. Participation in the study is completely voluntary, and patients are free to leave the study at any time.

6.2 Protection of Human Subjects

The investigators will take specific protections against these risks. Patients will be advised to contact the appropriate study Principal Investigator and/or IRB with any questions, concerns or complaints associated with their participation. Study coordinators will be available by email and phone to discuss any issues or uncomfortable questions that arise or if patient have problems associated with the use of Orchestra or another third-party device or application.

